The absorption and disposition parameters will be determined using a noncompartmental approach, trapezoidal rule will be used to estimate the area under the curve. The PK parameters of interest for this study will be:

Day 14 and Day 21: $T_{\max(ss)}$, $C_{\max(ss)}$, $AUC_{0-12(ss)}$, $AUC_{0-24(ss)}$, $C_{\min(ss)}$.

For Part B of study, plasma concentration data generated from sparse samples (maximum of 4 time points from each subject) on Day 14 and Day 21 will be used for calculation of PK parameters: $C_{\max(ss)}$, $AUC_{(ss)}$, $C_{\min(ss)}$.

Disease severity: Disease severity will be assessed by the Investigator's Global Assessment (IGA) score. Inflammatory and non-inflammatory lesion count (% change from baseline for both parameters) will also be done.

Safety:

Safety assessments will include adverse events (AEs), the investigator's assessment of application site reactions (dryness, non-lesional erythema, peeling, stinging, burning, and itching), clinical safety laboratory evaluations (chemistry, hematology, and urinalysis), and physical examination including vital signs (blood pressure and pulse rate).

Statistics:

Statistical analysis of all PK parameters will be based on analysis of variance (ANOVA) model. Two-sided 90% confidence intervals of the ratio of geometric least squares (LS) means will be presented from the natural log (ln)-transformed PK parameters ($C_{\max(ss)}$, $AUC_{(ss)}$, $C_{\min(ss)}$) for Test vs Reference on Day 14 and Day 21.

Achievement of steady state will be performed by treatment, using log-transformed $C_{\min(ss)}$ (at Days 12, 13 and 14 and Days 19, 20 and 21) in a mixed effect model through repeated-measure ANOVA or through other appropriate statistical method.

Disease severity will be assessed between baseline and sampling days by paired t-test or other appropriate statistical test and will be presented by treatment.

Descriptive statistics will be presented for safety parameters.

Table 1: Overall Study Procedure and Schedule of Assessments

Procedure or Assessment	Screening Visit	Treatment Application (21 Days)									
	(Day -21 to Day -1)	Baseline Visit (Day 1)	2 to 6	7	8 to 11	12 to 13	14	15 to 19	20	21	22
Informed consent/assent	X										
Inclusion and exclusion criteria	X	X									
Medical history / prior medications	X	X ¹									
Randomization		X									
Demographics	X										
Study drug administration ²		X	X	X	X	X	X	X	X	X	X ²
Confinement ³		X					X			X	
IGA assessment ⁴	X	X						X		X	X ⁴

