Subjects will visit the clinical site daily prior to each dose application. Subjects will be confined at the clinic on Day 1 from prior to the evening dose until after that dose, from prior to the evening dose on Day 14 to after the evening dose on Day 14, and from prior to the evening dose on Day 21 to after the 24-hour post dose PK sample collection on Day 22. Subjects will leave the clinic after completion of clinical activities. On Days 14 and 21, blood sampling for PK estimation will be performed over an interval of 24 hours. Adequate trough samples will be collected at the evening visit on Day 1 to assess baseline and on days 12, 13, 14, 19, 20 and 21 to assess attainment of steady state. For the pediatric population in part B, the trough samples will not be collected on days 12, 13, 19 and 20. Any subject missing dosing of any one dose of Reference product and two consecutive doses of Test product between days 1 and 8, or between days 8 and 15 will be considered for steady state estimation at Day 14, or Day 21, respectively. Subject (s) missing either two consecutive dosing days (two doses for reference and four for test product) between day 1 and 8 or missing two non-consecutive dosing days between Day 2 and Day 11 will be assessed for steady-state estimation at Day 21. Subjects missing dosing between Days 12 and 14 and between Days 19 and 21 will not be considered for steady-state estimation or PK and statistical analysis.

For all dosing days (except confinement days), subjects will come to the clinical site ± 1 hour of each dose application (e.g., around 7:00 pm and 7:00 am) for twice-daily application of Test product and (e.g. around 7:00 pm) for once-daily application of Reference product. Subjects will leave the clinical site after completion of the scheduled activities. On Day 14 and Day 21, subjects will report to the clinical site before scheduled dosing, allowing sufficient time for all pre-dosing assessments to be performed.

Blood samples for PK estimation will be collected (within time window ± 15 minutes) at scheduled intervals over a period of 24 hours after the evening dose application for Test product and Reference product on Day 14 and Day 21. On Day 22, for assessment of leave on exposure for 12 hours, the last dose application of Test product (morning dose on Day 22) will not be rinsed off.

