Study staff should wear gloves at all times while handling or applying the study product. If powdered gloves are worn, they should be rinsed and dried prior to handling study product.

Test Product

The Test product will be applied twice daily, 12 hours apart (± 1 hour) (morning and evening), for 21 days (42 consecutive doses). Before each dose application, subjects will take a brief warm shower to wet their skin. Approximately 5 grams of the product will be applied by the subject to the face, neck, and upper chest and will be applied by a member of the clinical staff to the shoulders and upper back, and rubbed into the skin until foamy (approximately 30 seconds for the total application area). After being left on for about 1 minute, the subject will rinse off the Test product in the shower for about 1 minute. On Day 22, the last dose application in morning will not be rinsed off in the shower; however, the subject will be permitted to towel dry after the Test product has been on for approximately one minute. Twelve hours following the last application,, the subject will rinse off in the shower for 1 minute. The subject should bare their exposed body parts when the product is rinsed off and the clinical staff should ensure that no residues are left on the body.

Note: For age group 9-11 years 11 months, approximately 4 grams of test product will be applied considering their lesser BSA.

Reference Product

The Reference product will be applied to dry skin once daily in the evening for 21 consecutive days. There should be a 24 hour interval between applications (± 1 hour). Approximately 5 grams of the product will be applied by the subject to the face, neck, and upper chest and by a

member of the clinical staff to the shoulders and upper back. The applied cream will be left on for 12 hours and showering will not be permitted until at least 12 hours after the application.

All Subjects

The times of dose applications should be recorded on the case report form (CRF).

Heavy make-up used to cover-up blemishes and sunscreen should be removed before study product application using a gentle cleanser approved by the investigator, such as Cetaphil Gentle Skin Cleanser, etc.

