2. On Day 21, update concomitant medications.
3. On Day 21 prior to evening dose application in evening for Test and Reference treatments, perform urine pregnancy test for female subjects, urine drug screen and alcohol breath test. Any subject with a positive alcohol breath test and/or positive drug screen should be discontinued.
4. On Day 21, perform 12-lead ECG pre-dose.
5. Prior to dosing on evening of Day 21 for Reference treatment and morning treatment of Day 22 for Test treatment, assess severity of acne by IGA scoring and measurement of lesion count. IGA scoring will be done prior to lesion count.
6. Prior to each dose application, visually inspect the skin and record erythema and scaling grades.
7. Apply assigned study product for the Day 21 evening dose application for Test and Reference treatments. For subjects assigned to Test treatment, the morning dose application will be performed the morning of Day 22 and this last dose application will not be rinsed off in the shower.
8. After each dose application, perform local cutaneous safety evaluation for dryness, non-lesional erythema, and peeling within 1 hour of dosing. The investigator or designated trained site staff should also ask the subject if any burning, stinging, or itching has occurred on the face since the last application. These evaluations should be recorded separately for the face and, if applicable, chest/back (including shoulders).
9. On Day 21, collect sitting vital signs (blood pressure and pulse) pre-evening dose and at 1 and 8 hours after evening dose application for Test and Reference treatments. (Note that the 8-hour post dose vital sign will occur on the morning of Day 22).
10. On Days 21 to 22, PK blood sample collection will occur at the following times:

In Part A (adults, age 17 years or older), blood samples will be collected prior (pre-dose) to the Day 21 evening dose application for Test and Reference treatments and at 1, 2, 4, 6, 8, 12, 14, 16, 18, and 24 hours post dose application.

In Part B for Test treatment (subjects age 9 years to 16 years 11 months) and Reference treatment (subjects 12 years to 16 years 11 months), a maximum of 4 blood samples will be collected as per the sparse sample design ([Table 3](#)).
11. On Day 21, collect blood sample for safety laboratory evaluations (chemistry, hematology, and urinalysis).
12. Collect AE data.
13. Complete CRF.

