11.1 Sample Size

Approximately 62 subjects will be enrolled in the study. Since the study is not aimed to meet the bioequivalence criteria, proper powering of the study is not required. The sample size chosen for the study attempts adequate representation of pediatric and adult population and was considered adequate to meet the study objectives.

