11.4 Pharmacokinetic Analyses

Tazarotene and tazarotenic acid plasma concentrations produced by the application of the study products will be determined to establish the PK profile of each treatment regimen. Below limit of quantitation concentrations (coded BLQ) will be treated as zero for all statistical analyses. The PK parameters will be derived from the plasma concentrations versus time profiles. All reported sampling time deviations following application for test and Reference will be taken into consideration for evaluation of PK parameters.

In the case where concentrations of tazarotene and tazarotenic acid cannot be determined due to bioanalytical or clinical reasons, these values will be set to missing for the PK and statistical analysis.

In the case where less than 3 consecutive measurable concentrations of tazarotene and tazarotenic acid are observed, the area under the curve (AUC) parameters will not be estimated for that specific study period.

The following PK parameters will be calculated for tazarotene and tazarotenic acid on Day 14 and Day 21 using a noncompartmental approach. The linear trapezoidal rule will be used to estimate the AUC.

$C_{\max(ss)}$:	Maximum observed maximum plasma concentration during a dosing interval at steady state
$AUC_{0-12(ss)}$	Area under the concentration–time curve from time zero to 12 hours post-dose, at steady state
$AUC_{0-24(ss)}$	Area under the concentration–time curve from time zero to 24 hours post-dose, at steady state
$T_{\max(ss)}$	Time to reach observed maximum plasma concentration, at steady state
$C_{\min(ss)}$	Minimum observed plasma concentration during a dosing interval at steady state

The absorption and disposition parameters will be determined using a noncompartmental approach, the trapezoidal rule will be used to estimate the area under the curve. The PK parameters of interest for this study will be:

Day 14 and Day 21: $T_{\max(ss)}$, $C_{\max(ss)}$, $AUC_{0-12(ss)}$, $AUC_{0-24(ss)}$, $C_{\min(ss)}$,

For Part B, plasma concentration data generated from sparse samples (maximum 4 time points from each subject) on Day 14 and Day 21 will be used for calculation of PK parameters: $C_{\max(ss)}$, $AUC_{(ss)}$, $C_{\min(ss)}$.

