Descriptive statistics will be calculated for plasma concentrations at each individual time point and for all PK parameters. The individual plasma concentration/time profiles will be presented using the actual sampling times whereas the mean plasma concentration/time profiles will be presented using the theoretical sampling times. Concentration/time profiles will be presented on linear and semi-log scales.

Pharmacokinetic analyses will be generated using validated PK software (e.g. Phoenix[®] WinNonlin[®] Version 6.3 or higher and Phoenix[®] Connect[™] version 1.3.1 or higher).

A statistical plan will be prepared. Statistical analysis of all PK parameters will be based on a parametric analysis of variance (ANOVA) model. Two-sided 90% confidence intervals of the ratio of geometric least squares (LS) means will be presented from the natural log (ln)-transformed PK parameters ($C_{\max(ss)}$, $AUC_{0-24(ss)}$, $C_{\min(ss)}$) for Treatment 1 vs Treatment 2.

Achievement of steady state will be performed by treatment, using log-transformed $C_{\min(ss)}$ (at Days 12, 13 and 14 and 19, 20 and 21) in a mixed effect model through repeated-measure ANOVA or through other appropriate statistical methods.

Disease severity will be assessed between baseline and sampling days by paired t-test or any other appropriate statistical test and will be presented by treatment.

Descriptive statistics will be presented for safety parameters.

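### Day 21 Test AUC0-24 combines one rinsed and one deliberately unrinsed dosing interval, yet is labelled steady state and enters a Day 21 Test/Reference ratio

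*Combined protocol and SAP*

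**What the plan says.** Section 6.2 has every Test dose left on for about one minute and then rinsed, with one exception. Section 4 says that, to assess 12-hour leave-on exposure, "the last dose application of Test product (morning dose on Day 22) will not be rinsed off". Section 7.10.4 repeats that "this last dose application will not be rinsed off in the shower". Section 6.2 adds that "the subject will be permitted to towel dry after the Test product has been on for approximately one minute", with rinsing 12 hours after application.

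Table 2 runs the Day 21–22 profile for 24 hours from the Day 21 evening dose. Section 11.4 calculates the PK parameters on Day 14 and Day 21, and defines AUC0-24(ss) as the area "from time zero to 24 hours post-dose, at steady state". It lists AUC0-24(ss), with Cmax(ss) and Cmin(ss), for two-sided 90% confidence intervals of the geometric mean ratio, without naming a day. The Synopsis (Statistics) gives the same kind of list, with AUC(ss) in place of AUC0-24(ss), "for Test vs Reference on Day 14 and Day 21".

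Cmax(ss) is defined as "Maximum observed maximum plasma concentration during a dosing interval at steady state", and Cmin(ss) is likewise tied to a dosing interval. Tmax(ss) and the Part B AUC(ss) have no stated window. No AUC12-24 or other leave-on parameter is named.

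**The concern.** The primary objective concerns twice-daily use of a product that, according to Section 1, is meant to be rinsed off after a minute. One altered application at the end of the study is not a steady state of that regimen. The Day 21 Test AUC0-24 is therefore half rinse-off and half leave-on, and estimates neither.

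Following the text as written, the Day 14 and Day 21 ratios would appear side by side under one (ss) label while answering different questions. A rise from Day 14 to Day 21 in the Test arm could be read as accumulation or a change in the skin barrier, and the Day 21 ratio as the ratio under intended use. The steady-state test on the Day 19, 20 and 21 troughs cannot show the problem, because all those samples precede the unrinsed dose. Meanwhile the leave-on assessment, which the protocol says it wants, has no parameter of its own.

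**Working it through.** **1. Where the unrinsed dose falls.** Sections 4 and 6.2 give 42 Test doses. Evenings of Days 1–21 (21) plus mornings of Days 2–22 (21) give 42, which reproduces the plan's figure. The Day 21 evening dose is no. 41 and the Day 22 morning dose is no. 42, about 12 h into the profile. With the ±1 h dosing window it falls at 11–13 h, so it governs (24−13)/24 = 46% to (24−11)/24 = 54% of the 24-hour window.

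**2. Which samples follow it.** In Part A (Table 2): 14, 16, 18 and 24 h, that is 4 of the 10 post-dose samples. In Part B (Table 3): the 18 and 24 h samples of subjects who give the late set on Day 21–22.

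**3. Effect on the ratio.** Let A be the Test AUC over one rinsed 12-hour interval, assumed equal for evening and morning doses, and let k be the leave-on AUC12-24 divided by the rinsed AUC over the same 12 hours.

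- Intended 24-hour value: A + A = 2A.
- Value obtained on Day 21: A + kA.
- Factor: (A + kA)/(2A) = (1+k)/2.

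The Reference regimen does not change on Day 21, so the Test/Reference ratio is multiplied by the same factor (taking k as common to all subjects):

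| k (assumed) | factor |
|---|---|
| 1 | (1+1)/2 = 1.00 |
| 1.25 | (1+1.25)/2 = 1.125 |
| 1.5 | (1+1.5)/2 = 1.25 |
| 2 | (1+2)/2 = 1.50 |

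**4. What k might be.** The documents give no leave-on effect, half-life or absorption rate. k is a ratio of AUCs, not of absorbed amounts, and carry-over from earlier rinsed doses pulls it towards 1. As an illustration only, with all inputs assumed: one compartment, 41 equal doses every 12 h, then dose 42 with a multiplied input, and the linear trapezoid on the Table 2 grid.

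| Input of dose 42 | ka (per h) | k (half-life 6 h / 18 h) | AUC0-24 factor (6 h / 18 h) |
|---|---|---|---|
| 1.5-fold | 0.5 | 1.33 / 1.16 | 1.17 / 1.08 |
| 2-fold | 0.5 | 1.67 / 1.31 | 1.33 / 1.16 |
| 2-fold | 0.1 | – | 1.18 / 1.08 |

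Changing one assumed rate constant roughly halves the excess, so these figures show a mechanism and do not estimate a size.

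**5. What is and is not affected.**

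- Day 14, all parameters: unaffected. No exception to rinsing is stated for the Day 15 morning dose.
- Day 21 AUC0-12: unaffected provided the 12 h sample is drawn before the morning dose. Dosing at 12 h ±1 h and sampling at 12 h ±15 min allow the sample to fall up to 12.25 − 11 = 1.25 h after dose 42. Section 7.10.3 fixes the order for the 24 h sample on Day 15; no passage fixes it for the 12 h sample.
- Day 21 Cmax and Cmin: exposed only if read over 0–24 h. In the illustration (2-fold input, ka 0.5), Cmax over 0–24 h is multiplied by 1.70 / 1.33, Cmax over 0–12 h by 1.00, and Cmin by 1.00.
- Part B AUC(ss): affected only if it covers 0–24 h on Day 21.

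**The case against.** The unrinsed dose is intentional and its purpose is stated. AUC0-12(ss) is already a planned Day 21 parameter, so the leave-on interval follows by subtraction: labels are missing, not data. No single sentence specifies a Day 21 AUC0-24 ratio; it comes from reading Section 11.4 (which names the window but no day) with the Synopsis (which names the day but no window). A separate SAP is announced in Sections 11 and 11.4; it is not part of the document under review and may settle this. Section 11.1 says that "the study is not aimed to meet the bioequivalence criteria", so no accept/reject decision turns on the ratio.

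All of that stands, and it limits the point. It does not remove it: Section 11.4 itself applies the steady-state definition to both days, and nothing in the text available separates the two intervals. In a study whose output is estimation, a mislabelled estimate is worth correcting.

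A reader might also infer that Day 21 Cmax and Cmin are distorted. For a product dosed every 12 hours, a dosing interval reads naturally as 0–12 h, and then neither is affected; Tmax is in neither ratio list. Nor do the documents support a claim that Part B late samples will be pooled across days: no pooling is stated.

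**Conclusion.** The point holds for the Day 21 Test AUC0-24, its (ss) label, its Day 21 Test/Reference ratio, and the missing leave-on parameter. It should be fixed, but it is a matter of definition and reporting.

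The size is unknown. The ratio is multiplied by (1+k)/2, assuming equal rinsed exposure after morning and evening doses, and k may be near 1 because subjects may towel dry after about a minute. A reader might set 12 hours of contact against 1 minute and infer a large inflation; the documents give no data linking contact time to exposure, so that does not follow. A reader might also infer that the primary comparison is lost. It is not: Day 14 AUC0-24 answers it, and Day 21 AUC0-12 is usable on the stated condition about the 12 h sample.

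**What to change.** In Section 11.4 and the SAP:

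1. Take the 24-hour rinse-off Test/Reference ratio from Day 14 AUC0-24. Remove (ss) from the Day 21 Test AUC0-24 and do not present its ratio as the rinse-off comparison.
2. On Day 21, report Test AUC0-12 and Cmax over 0–12 h as rinse-off. Test AUC0-12 alone is not a daily exposure to set against a once-daily Reference. If a daily Day 21 contrast is wanted, including for subjects deferred to Day 21 after missed doses (Sections 4 and 6.3), use 2 × Test AUC0-12 against Reference AUC0-24 as a supportive analysis, stating the assumption of equal morning and evening rinsed exposure. The Part A Day 14–15 profiles allow that assumption to be checked.
3. Report Day 21–22 Test AUC12-24 and Cmax12-24 as separately labelled leave-on parameters. Any within-subject comparison with Day 14–15 should be descriptive and in Part A only, since each Part B subject has the 12, 18 and 24 h samples on just one of the two days. It is confounded with a further week of treatment and possible skin-barrier change, which Section 4 gives as the reason for choosing Day 14.
4. State the Test-arm window for Cmax, Tmax and Cmin and the window for Part B AUC(ss), and state that the 12 h sample precedes the morning dose. For Part A, check this from recorded application and sampling times.
5. Record that this rule was set after Part A PK was assessed (Section 7.5).

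Cost: text changes and one sampling-order instruction to sites for Part B subjects still to be sampled; no new samples. Downsides: no directly observed 24-hour rinse-off exposure on Day 21, reliance on the equal-interval assumption for any Day 21 daily contrast, and a rule made after Part A data were seen.

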5 SELECTION OF STUDY POPULATION

5.1 Number of Subjects

Approximately 62 subjects across 2 study sites will be enrolled.

5.2 Inclusion Criteria

1. Subject understands the study procedures, is willing to comply with the study procedures and required visits, and agrees to participate by giving written informed consent. Subjects under the legal age of consent must provide written assent and must have the written informed consent of their legal guardian.
2. Subject (or legal guardian) must be willing to authorize use and disclosure of protected health information collected for the study.
3. Male or female at least 9 years of age for the DFD-03 (Test) group and at least 12 years of age for the Tazorac Cream (Reference) group.
4. Female subjects must be having their menstrual period at Baseline (Day 1, as reported by the subject), except for subjects using hormonal contraceptives that preclude menstrual periods, if the subject is premenarcheal, is postmenopausal for at least 12 months prior to

- baseline, is surgically sterilized (i.e., tubal ligation), or if the subject is without a uterus and/or both ovaries.
5. A clinical diagnosis of facial acne vulgaris with a facial Investigator's Global Assessment (IGA) score of 3 (moderate) at Baseline (Day 1).
 6. Subjects should have acne lesions on at least 1 of the following regions at the Screening visit: neck, upper chest, upper back(including shoulders).
 - This criterion is not applicable to the 9-11 years and 11 months age group.
 7. Inflammatory lesion count (papules and pustules) of at least 20 on the face, including the nose, at Baseline visit (Day 1).
 - This criterion is not applicable to the 9-11 years and 11 months age group.
 8. Non-inflammatory lesion count (closed and open comedones) of at least 25 on the face, including the nose, at Baseline (Day1).
 - This criterion is not applicable to the 9-11 years and 11 months age group.
 9. No more than 2 nodulocystic lesions on the face, including the nose, at Baseline (Day 1).
 10. Females, regardless of childbearing potential:
 - a. Must have a negative serum pregnancy test at Screening and a negative urine pregnancy test at Baseline (Day 1). Urine pregnancy test must have a sensitivity of at least 25 mIU/mL for beta human chorionic gonadotropin (β hCG).
 - b. If sexually active, must be on or use an acceptable method of birth control.

Acceptable methods of birth control include: hormonal methods* or intrauterine device in use \geq 90 days prior to Baseline (Day 1); or partner has had a vasectomy at least 90 days prior to Baseline (Day 1); or barrier methods plus spermicide; or Essure[®] that has been in place for at least 3 months before the screening visit with radiograph confirmation of fallopian tube blockage.

***Hormonal methods:** If on hormonal contraceptives, must have been on the same hormonal contraceptive product for 3 months (90 days) prior to Baseline (Day 1) and continued on same method and dose throughout the duration of the study. If subject had used hormonal birth control and had stopped, this should have occurred more than 6 months prior to Baseline.

Exception: Sexually inactive female subjects are not required to practice a reliable method of contraception and may be enrolled at the investigator's discretion if they are counseled to remain sexually inactive for the duration of the study and understand the possible risks involved in getting pregnant during the study. An abstinent female must agree that if she becomes sexually active during the study she will use an acceptable form of contraception such as a barrier method with spermicide.
 11. Subjects agree not to use any product on the face during the entire course of study except for non-medicated, investigator-approved cleanser, sunscreen, face wash, and make-up. Subjects should continue to use these investigator-approved products for the duration of the study and should avoid any changes in these consumer products.

12. Subjects must be willing to comply with sun avoidance measures for the face (as well as back/chest and shoulders, if applicable) including use of investigator-approved sunscreen and/or hats, have limited direct sunlight exposure time, and have no tanning bed use or use of other UV light sources during participation in the study.
13. Subject must be in good general health as determined by the investigator and supported by the medical history, physical examination, and normal or not clinically significant abnormal vital signs (blood pressure and pulse).

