4 STUDY DESIGN

This will be a randomized, multiple-dose, laboratory-blinded, open-label, 2-arm, parallel-arm, multicenter study in subjects with moderate acne vulgaris.

Approximately 62 subjects will be randomized to receive either Test or Reference product, stratified by age (adult subjects: 17 years or older; pediatric subjects: 9 years to 16 years 11 months for the Test product and 12 years to 16 years 11 months for the Reference product) with approximately even distribution between males and females in each age stratum. The study will be conducted in two parts, Part A and Part B in a sequential manner. Based on full PK profiles generated for adult subjects in Part A, the sparse PK sampling design in pediatric subjects has been established in Part B. Part B (age 9 years to 16 years 11 months for DFD-03 and 12 years to 16 years 11 months for Reference) will enroll up to 38 subjects, which will include at least 6 subjects 9 to 11 years of age, and among those at least 2 subjects between 9 and 10 years of age. Target enrollment is 32 subjects, but up to 6 additional subjects may be enrolled to reach a minimum of 16 evaluable subjects, who have sparse samples collected on Day 14 and Day 21, randomized to the Test treatment.

PK profiling will be performed on Day 14 and on Day 21. Day 14 is selected as the earliest time point at which the steady state is expected to be achieved in subjects with moderate acne vulgaris, before any significant improvement in skin barrier occurs.

In Part A, 24 adult subjects will be enrolled such that 12 subjects each will be assigned to receive either Test or Reference treatment. In Part B, up to 38 subjects will be enrolled where approximately 26 subjects will receive Test treatment and 12 subjects will receive Reference treatment. Enrollment will continue until at least 16 evaluable subjects randomized to the Test treatment complete the study.

For 21 days, study product will be applied on the face, neck, upper chest, shoulders and upper back region, not exceeding 15% of the body surface area. The Test product will be applied twice daily, 12 hours apart (morning and evening; 42 consecutive doses), and the Reference product will be applied once daily in the evening (21 consecutive doses).

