6.4 Method of Assigning Subjects to Treatment Groups

Each subject will be assigned a unique identification number upon screening. Subjects who complete the study screening assessments and meet all eligibility criteria will receive the treatment as per randomization, the order of which will be according to randomization scheme generated for each site.

The investigator shall ensure that study products are only used by subjects under investigator supervision or under supervision of sub-investigator, responsible to investigator and in accordance to the study protocol.

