11.2.2 Pharmacokinetic Analysis Population

Samples from all subjects who provide evaluable data will be assayed; these subjects will be included in the PK and statistical analysis. In order to be considered evaluable, a subject must have PK samples collected on both Day 14 and Day 21. An unequal number of subjects per arm will be used.

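### Ages 9 to 11 can only receive Test, yet the stated PK population and ANOVA ratio do not set them apart, so a Test/Reference ratio that includes them mixes product with age, body size, applied amount and entry criteria

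*Combined protocol and SAP*

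**What the plan says.** Section 5.2, criterion 3, sets the minimum age by arm: "at least 9 years of age for the DFD-03 (Test) group and at least 12 years of age for the Tazorac Cream (Reference) group". Section 4 carries this into the pediatric stratum: "pediatric subjects: 9 years to 16 years 11 months for the Test product and 12 years to 16 years 11 months for the Reference product". Part B enrols up to 38 subjects, "which will include at least 6 subjects 9 to 11 years of age"; no maximum is given for that group. Section 6.2 has about 4 g of Test applied at ages 9 to 11 years 11 months, against about 5 g for everyone else, and gives smaller body surface area as the reason. Section 5.2 exempts the same group from criteria 6, 7 and 8 (lesions beyond the face, and the minimum inflammatory and non-inflammatory facial counts).

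On assignment, section 4 says: "Approximately 62 subjects will be randomized to receive either Test or Reference product, stratified by age". Section 6.4 says that eligible subjects "will receive the treatment as per randomization, the order of which will be according to randomization scheme generated for each site". No separate route is described for children who cannot be given Reference.

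On analysis, section 11.2.2 says: "Samples from all subjects who provide evaluable data will be assayed; these subjects will be included in the PK and statistical analysis". The synopsis says: "Statistical analysis of all PK parameters will be based on analysis of variance (ANOVA) model", with 90% confidence intervals for Test against Reference on Days 14 and 21. Section 11.4 repeats the ANOVA but compares two numbered treatments that it does not define. Neither place gives model terms, an age limit, or a rule on whether Part B is pooled with Part A, compared separately or only described. A separate SAP is promised in section 11 but is not among the documents supplied.

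**The concern.** Comparative bioavailability is the primary objective, and the Test/Reference ratio of geometric means is its estimate. Randomisation protects that ratio only among subjects who could have received either product. Children aged 9 to 11 could not. They also differ from the remaining Test subjects in body size, applied amount and severity at entry, and the Reference arm has no counterpart in any of these respects. A Test/Reference ratio for ages 9 to 11 cannot be estimated from this design, and including them in a wider ratio adds a difference that is not due to product.

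The natural safeguard, adjusting for the randomisation stratum, does not help, because the pediatric stratum holds ages 9 to 11 together with ages 12 to 16. The Part B enrolment floor is not age-limited either: enrolment may be extended to "reach a minimum of 16 evaluable subjects, who have sparse samples collected on Day 14 and Day 21, randomized to the Test treatment". If six of those 16 are aged 9 to 11, only 10 Test subjects aged 12 to 16 remain to set against 12 on Reference.

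**Working it through.** **The plan's own total.** Part A 12 + 12, Part B about 26 + 12: 12 + 12 + 26 + 12 = 62, as stated. No variance, effect size or margin is given, so nothing else can be reproduced.

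**Share of the Test arm aged 9 to 11**, taking exactly six, all evaluable:
- Part B: 6/26 = 23.1%; 6/16 = 37.5% at the evaluable floor.
- Pooled with the 12 adult Test subjects: 6/38 = 15.8%; 6/28 = 21.4%.
- Reference: 0% throughout.

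**Effect on the ratio.** Let r be exposure at ages 9 to 11 relative to other Test subjects on the same product. The documents give no value, so r from 0.5 to 2.0 is an assumption, symmetric on the log scale because the direction is unknown. With share s, the geometric mean ratio is multiplied by r^s.

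| Comparison | s | r = 0.5 | r = 0.8 | r = 1.25 | r = 2.0 |
|---|---|---|---|---|---|
| Part B, 16 on Test | 6/16 | 0.771 | 0.920 | 1.087 | 1.297 |
| Part B, 26 on Test | 6/26 | 0.852 | 0.950 | 1.053 | 1.173 |
| Pooled, 28 on Test | 6/28 | 0.862 | 0.953 | 1.049 | 1.160 |
| Pooled, 38 on Test | 6/38 | 0.896 | 0.965 | 1.036 | 1.116 |

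At r = 1 every factor is 1.00.

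**Does the existing stratum remove it?** In an additive model with treatment and the two-level stratum, each stratum's Test-minus-Reference difference is weighted by nT × nR/(nT + nR).
- Adults: 12 × 12/24 = 6.
- Part B with 26 on Test: 26 × 12/38 = 8.21. Its weight is 8.21/14.21 = 0.578, so the exponent is 0.578 × 6/26 = 0.133. The factor is 0.912 at r = 0.5 and 1.097 at r = 2.0.
- Part B with 16 on Test: 16 × 12/28 = 6.86. Its weight is 6.86/12.86 = 0.533, so the exponent is 0.533 × 6/16 = 0.200. The factor is 0.871 at r = 0.5 and 1.149 at r = 2.0.

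Most of the shift remains. Limiting the ratio to ages 12 and over gives 1.00 for every r.

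**Precision cost of the restriction.** 90% CI factor = exp{t(0.95, n1 + n2 − 2) × √ln(1 + CV²) × √(1/n1 + 1/n2)}. The between-subject CV is assumed to be 40% to 100%.

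| Part B, Test v Reference | CV 40% | CV 100% |
|---|---|---|
| 26 v 12 | 1.255 | 1.633 |
| 16 v 12 | 1.285 | 1.720 |
| 20 v 12 (26 less six) | 1.270 | 1.675 |
| 10 v 12 (16 less six) | 1.329 | 1.849 |
| 10 v 9 (illustrative Reference loss) | 1.361 | 1.945 |

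**Bias against imprecision.** The shift equals the CI factor when r = (CI factor)^(1/s). At CV 40% that is r = 1.95 (16 on Test) or 2.67 (26 on Test); at CV 100% it is 4.25 or 8.38.

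**The case against.** The strongest reply is that model terms, pooling and age handling are ordinary SAP content, and a SAP is promised before database lock. Nor does any sentence say outright that ages 9 to 11 enter a single ANOVA with older subjects. The population statement in 11.2.2 also covers descriptive summaries, and the age groups sit in sequential Parts with different sampling and parameter lists. Section 11.4 names AUC0-24 for the ratio, while the Part B list has only an AUC without an interval, so a Part A-only ratio is a fair reading for AUC. That stands for AUC in 11.4. It does not settle the matter: Cmax and Cmin are in both lists, the synopsis ratio uses the AUC without an interval, and the only population rule written down has no age limit.

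A reader might infer that the sponsor will compute a confounded ratio, or that Test exposure will be overstated. The documents support neither. The unseen SAP may deal with the point. The direction is unknown, since smaller body size and the smaller applied amount may partly offset each other.

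The precision figures are also idealised. On a given PK day a Part B subject is sampled either at 0, 2 and 8 hours or at 4, 12, 18 and 24 hours, so one equally informative AUC per subject is optimistic. The 16 v 12 and 10 v 12 cases assume no Reference loss, although section 7.7 does not replace withdrawals and no Reference floor is stated. The 10 v 9 row shows that the cost of the fix could be higher.

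**Conclusion.** The point holds as a gap in the protocol: followed as written, the plan allows subjects who could receive only Test to enter the primary ratio, and adjusting for its own age stratum would not correct that. With exactly six evaluable and r assumed between 0.5 and 2.0, a Part B ratio is multiplied by 0.77 to 1.30 (16 on Test) or 0.85 to 1.17 (26 on Test). A pooled ratio is multiplied by 0.86 to 1.16 (28 on Test) or 0.90 to 1.12 (38 on Test). More than six would raise the share. A ratio from Part A alone is unaffected.

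It would be too strong to say that a bioequivalence conclusion is endangered. Section 11.1 says the study does not aim to meet bioequivalence criteria, and no acceptance limit is stated; the harm is to interpretation of the ratio. It would also be too strong to say that bias outweighs sampling error, because at the assumed CVs exposure would have to differ roughly two- to eight-fold for the two to be equal. The omission is certain and its consequence is not. It should be fixed because the remedy is cheap and removes this source of bias whatever r is.

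**What to change.** In the synopsis, sections 11.2.2 and 11.4, and the SAP before database lock: base any Test/Reference ratio on subjects aged 12 and over, by stratum (12–16; 17 and older). Put stratum in the ANOVA if the two are combined, and summarise ages 9 to 11 years 11 months descriptively as a Test-only cohort. In the synopsis and sections 4 and 6.4, describe that cohort as non-randomised and say how its members are assigned. State whether the floor of 16 evaluable Test subjects counts them.

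Other choices are defensible. A three-level age term (9–11; 12–16; 17 and older) gives the same treatment estimate as exclusion, provided the model has no other covariates. Restriction is simpler to state.

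The cost is wording and one population flag, with no extra subjects. If the per-site randomisation scheme already includes ages 9 to 11, its handling must be documented; the documents do not show this. A Part B ratio loses about six Test subjects, so its 90% CI factor goes from 1.255–1.72 to 1.27–1.85 (26 or 16 v 12 becomes 20 or 10 v 12, CV 40–100%), or to 1.36–1.95 at 10 v 9, under the idealised assumptions noted above. No view is taken on the applied amount.
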